## **5. Product Features, Structural Composition, Operating Principle, Action Mechanism and Test Scope**

### **5.1 Product Features**

Expanded hemodialysis (HDx), enabled by the Theranova dialyzer, expands the range of uremic solutes (up to 45,000 Da) efficiently removed during intermittent HD.

The Theranova dialyzer provides removal of small molecules (<500 Da, such as urea) equivalent to high flux membranes used in HD and HDF. Removal of conventional middle molecules (500 - <25,000 Da, such as  $\kappa$  FLC) is increased compared to high flux membranes used in HD. Removal of large middle molecules (25,000 – 45,000 Da, such as  $\lambda$  FLCs) is increased compared to high flux membranes used in HD and HDF.

Expanded hemodialysis, enabled by the Theranova dialyzer, achieves its performance using existing HD workflow and infrastructure.

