### **8.3 Significance Level and Power of Clinical Study**

A 0.025 one-sided significance level and a power of 90% were used in planning this study.

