### **8.5 Eligibility/Fail Criteria for Clinical Study Results**

Let  $\mu_T$  denote the Theranova 400 treatment mean and let  $\mu_R$  denote the FX 800 treatment mean. The statistical hypothesis of the study can be written as:

$$H_0: \mu_T - \mu_R \leq -\delta$$

$$H_a: \mu_T - \mu_R > -\delta$$

When evaluating the primary endpoint of  $\lambda$  FLC, the non-inferiority margin is -3.783 (10% of assumed mean RR of 37.83%). When evaluating the primary endpoint of  $\beta$ 2-MG RR, the non-inferiority margin is -7.848 (10% of assumed mean reduction ratio of 78.48%). When the non-inferiority of the two primary endpoints of  $\lambda$  FLC and  $\beta$ 2-MG RRs are both established, the non-inferiority of this study is established.

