## **8.7 Statistical Methods of all Data, together with Processing of Missing, Unused or Erroneous data (including midway exit and withdrawal) and Unreasonable Data**

### **8.7.1 Data Statistical Analysis**

#### **8.7.1.1 Analysis of Primary Endpoints**

For the  $\lambda$  FLC and  $\beta2$ -MG RR endpoints, let  $\mu_T$  denote the TheraNova 400 treatment mean and let  $\mu_R$  denote the FX 800 treatment mean. Then the null hypothesis to demonstrate non-inferiority using a 10% margin for  $\lambda$  FLC RR can be expressed as:  $H_0: \mu_T - \mu_R \leq -3.783$ . The alternative hypothesis is expressed as:  $H_a: \mu_T - \mu_R > -3.783$ . A t-test will be utilized to generate a two-sided 95% confidence interval (CI) for the difference in means ( $\mu_T - \mu_R$ ). If the lower bound of the CI is  $> -3.783$ , then non-inferiority between the TheraNova 400 and FX 800 treatment group can be demonstrated for  $\lambda$  FLC RR. If the lower bound of the CI  $> 0$ , then superiority of TheraNova 400 treatment over FX 800 treatment can be concluded.

Equivalently the null hypothesis to demonstrate non-inferiority using a 10% margin for  $\beta2$ -MG RR can be expressed as  $H_0: \mu_T - \mu_R \leq -7.848$ . The alternative hypothesis is expressed as:  $\mu_T - \mu_R > -7.848$ . A t-test will be utilized to generate a two-sided 95% confidence interval (CI) for the difference in means ( $\mu_T - \mu_R$ ). If the lower bound of the CI is  $> -7.848$ , then non-inferiority between the TheraNova 400 and FX 800 treatment group can be demonstrated for  $\beta2$ -microglobulin RR. If the lower bound of the CI  $> 0$ , then superiority of TheraNova 400 treatment over FX 800 treatment can be concluded.

Two sensitivity analysis will be conducted for both endpoints:

1. An ANOVA model with fixed effects for treatment group and study site to evaluate differences between the treatment groups will be analyzed and corresponding two-sided 95% CIs derived.

A non-parametric method: Wilcoxon Rank-Sum Test will be used to analyze the primary endpoints.

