### **7.5 Statistical Tests**

Unless specified, all statistical tests will be performed at a significance level of 5% with two-sided 95% confidence interval (CI).

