### 8.2 Multiple Comparisons / Multiplicity

The two primary endpoints will be tested simultaneously. Only when both primary endpoints pass is the study declared successful. Therefore, no multiplicity adjustment are necessary for this portion. Hierarchical structure will be used for the testing for both non-inferiority and superiority. Superiority will only be tested if non-inferiority passes.

There are no other multiplicity adjustments are made for the study. The secondary endpoint is not assigned to alpha, so it not refers to alpha adjustment. All secondary endpoints, all p values are descriptive in nature only.

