### 17.1.2 Primary Analysis Of Primary Efficacy Variables

PPS population is the primary efficacy analysis population. Descriptive statistics of reduction ratios of  $\lambda$  FLC and  $\beta 2$ -MG will be provided by treatment group.

Listings of reduction ratio will be presented and sorted by patient id and treatment group.

The statistical hypothesis for testing the treatment group difference for reduction ratios of  $\lambda$  FLC is presented as follows:

- $H_0: \mu_T - \mu_R \leq -3.783$  tested against the alternative hypothesis
- $H_a: \mu_T - \mu_R > -3.783$

where:

$\mu_T$  is the means of RRs of  $\lambda$  FLC in Theranova 400 treatment and  $\mu_R$  is the means of RRs of  $\lambda$

FLC in the FX 800 treatment.

A two-sample t-test will be utilized to generate a two-sided 95% confidence interval (CI) for the difference in means ( $\mu_T - \mu_R$ ). If the lower bound of the CI is greater than -3.783, then non-inferiority between the Theranova 400 and FX 800 treatment group can be demonstrated for  $\lambda$  FLC RR. If the lower bound of the CI is greater than zero, then superiority of Theranova 400 treatment over FX 800 treatment can be concluded.

The statistical hypothesis for testing the treatment group difference for reduction ratios of  $\beta 2$ -MG is presented as follows:

- $H_0: \mu_T - \mu_R \leq -7.848$  tested against the alternative hypothesis
- $H_a: \mu_T - \mu_R > -7.848$

where:

$\mu_T$  is the means of RRs of  $\beta 2$ -MG in Theranova 400 treatment and  $\mu_R$  is the means of RRs of  $\beta 2$ -MG in the FX 800 treatment.

A two-sample t-test will be utilized to generate a two-sided 95% confidence interval (CI) for the difference in means ( $\mu_T - \mu_R$ ). If the lower bound of the CI is greater than -7.848, then non-inferiority between the Theranova 400 and FX 800 treatment group can be demonstrated for  $\beta 2$ -MG RR. If the lower bound of the CI is greater than zero, then superiority of Theranova 400 treatment over FX 800 treatment can be concluded.

The two hypothesis tests are hierarchically structured so that the second test (superiority) will only be considered if the first test (non-inferiority) is rejected. There is no alpha adjustment for the second test as a result of the hierarchical testing.

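### Superiority can be concluded from either primary endpoint alone, each at one-sided 2.5%, and the reason given for not adjusting alpha covers only one endpoint

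*SAP*

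**What the plan says.** **Test level.** Protocol 8.3 states: "A 0.025 one-sided significance level and a power of 90% were used in planning this study". SAP 7.5 uses two-sided 95% intervals, so reading the lower bound alone is a one-sided 2.5% test.

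**Non-inferiority.** Both endpoints must succeed. Protocol 8.5 says that when they do, "the non-inferiority of this study is established". SAP 8.2 gives the same rule as its reason for not adjusting alpha, and limits that reason to this part of the testing.

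**Superiority.** SAP 17.1.2 and Protocol 8.7.1.1 set a rule under λ FLC and repeat it under β2-MG: if the lower bound exceeds zero, "then superiority of TheraNova 400 treatment over FX 800 treatment can be concluded" (Protocol wording; the SAP's is the same in substance). In both documents the non-inferiority sentence just before it ends by naming the marker. The superiority sentence does not.

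**Link between the two.** SAP 8.2 says: "Superiority will only be tested if non-inferiority passes". It does not say whether this means the endpoint's own non-inferiority result or both. SAP 17.1.2 draws the conclusion: "There is no alpha adjustment for the second test as a result of the hierarchical testing". SAP 8.2 closes the matter: "There are no other multiplicity adjustments are made for the study". Neither document orders the two superiority tests, splits alpha between them, or requires superiority on both.

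**The concern.** The SAP gives two reasons for leaving alpha unadjusted. Each is sound for its own purpose, but neither reaches this case.

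- The both-must-pass rule controls error for the pair of non-inferiority tests.
- The order of non-inferiority then superiority controls error for two nested hypotheses on one endpoint.

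Two superiority tests, either of which permits a conclusion, are a different family. Their joint error exceeds the per-test level unless something links them.

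What is at stake is a superiority statement over HDF, not the study's main conclusion. Superiority appears in none of the objectives. However, the plan writes a formal decision rule for it inside the primary analysis. SAP 8.2 calls the secondary-endpoint p-values descriptive but does not say so of superiority on the primary endpoints. Protocol 5.1 already says that removal of large middle molecules, with λ FLC as the example, "is increased compared to high flux membranes used in HD and HDF", so the plan itself gives a context in which such a statement would matter.

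**Working it through.** **Inputs.** Margins 3.783 and 7.848 (Protocol 8.5); planning SDs 9.09 and 14.28, true difference 0, 129 evaluable per arm (SAP 3.2); one-sided 0.025 (Protocol 8.3). The correlation between the two test statistics is in neither document, so it is varied from 0 to 0.9.

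**The plan's own figures reproduce.** n per arm = 2 × SD² × (1.960 + 1.282)² / margin².

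- λ FLC: 2 × 9.09² × 10.51 / 3.783² gives 122. The t-test version is 123, and multiplying by π/3 for the Wilcoxon test gives 129, as stated.
- β2-MG: 2 × 14.28² × 10.51 / 7.848² gives 70. The t-test version is 71, and π/3 gives 75, as stated.
- 129 / 0.95 gives 136 per arm, 272 in total, as stated.

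**Step 1: either endpoint suffices.** With both true differences zero,

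P(at least one false claim) = 0.025 + 0.025 − P(Z1 > 1.96 and Z2 > 1.96).

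At correlation 0 this is 0.05 − 0.025² = 0.0494. At other correlations the last term comes from the bivariate normal distribution; at 0.9 it is 0.0148, giving 0.0352.

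Requiring the endpoint's own non-inferiority first changes nothing, because a lower bound above zero already lies above the margin.

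**Step 2: non-inferiority required on both endpoints first.** The standard errors are 9.09 × √(2/129) = 1.132 and 14.28 × √(2/129) = 1.778. Non-inferiority passes if Z1 > 1.96 − 3.783/1.132 = −1.38 and Z2 > 1.96 − 7.848/1.778 = −2.45. The quantity needed is the probability that both hold and at least one Z exceeds 1.96.

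**Step 3: remedies.** With the Step 2 precondition and a fixed order (λ FLC first), a false claim needs Z1 > 1.96. Under Holm it needs at least one Z above 2.2414 (one-sided 0.0125); the Holm column is computed without the precondition.

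| Correlation (assumed) | Either suffices | Both non-inferior first | Both non-inferior first, then fixed order | Holm |
|---|---|---|---|---|
| 0 | 4.94% | 4.71% | 2.48% | 2.48% |
| 0.3 | 4.76% | 4.72% | 2.50% | 2.42% |
| 0.5 | 4.54% | 4.53% | 2.50% | 2.32% |
| 0.7 | 4.17% | 4.17% | 2.50% | 2.15% |
| 0.8 | 3.90% | 3.90% | 2.50% | 2.01% |
| 0.9 | 3.52% | 3.52% | 2.50% | 1.81% |

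A simulation with t-based intervals (400,000 runs) for the third column gave 4.67% at correlation 0 and 3.91% at 0.8.

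**Step 4: what Holm costs.** The observed difference needed to conclude superiority at Holm's opening step rises from 1.96 × 1.132 = 2.22 to 2.2414 × 1.132 = 2.54 points for λ FLC, and from 1.96 × 1.778 = 3.48 to 2.2414 × 1.778 = 3.99 points for β2-MG.

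**The case against.** The strongest reply is that the superiority sentences are marker-specific in context. Each closes a paragraph that defines the two means for one solute and refers to that solute's interval, and each endpoint gets its own descriptive statistics. Nothing in the plan pools the two into an explicit either-or rule. On that reading, 2.5% per marker could be defended, and only the omitted name needs repair.

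This reading is fair, but it does not remove the problem. It still leaves two confirmatory superiority claims with no control across them. The reason the SAP gives for that is the hierarchy, which does not supply such control. A per-marker policy would need to be stated as such.

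Two further objections stand in part:

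- No passage sets a family-wise level for superiority, so 2.5% as the benchmark is the per-test level carried over, not a promise the plan breaks.
- The 4.9% figure requires zero correlation. Both ratios come from the same patient and session, so a positive correlation is more plausible and the true figure is probably lower. It stays above 2.5% at every value examined.

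The unclear precondition is worth tidying, but it has little numerical effect: 4.94% against 4.71% at correlation 0, and no visible difference from 0.7 upward.

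**Conclusion.** The concern holds. As written, one marker is enough to conclude superiority, and the stated ground for no adjustment does not extend to two endpoints. If the devices are equal on both markers, the chance of at least one false superiority conclusion lies between 3.5% and 4.9% for correlations from 0.9 down to 0. Requiring non-inferiority on both endpoints first barely changes that.

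These figures rest on an assumed correlation, on normal approximations and, for the version with the precondition, on the planning SDs with 129 per arm. The non-inferiority conclusion keeps its one-sided 2.5% error rate. This is something that should be corrected before a superiority statement is made; it does not threaten the primary result.

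**What to change.** Amend SAP 8.2, SAP 17.1.2 and Protocol 8.7.1.1 as follows:

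1. State that superiority is tested only after non-inferiority has been shown on both endpoints.
2. Pre-specify a fixed order, each test at one-sided 0.025. For example, take λ FLC first, the marker for which Protocol 5.1 expects greater removal than with HDF, and β2-MG only if λ FLC succeeds. Holm across the two endpoints is the alternative.
3. Name the endpoint in each superiority statement.

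The changes are to wording. Sample size and the non-inferiority tests stay as they are. Under the fixed order, a β2-MG superiority claim is lost if λ FLC is not superior. Under Holm, superiority at the opening step needs the larger observed difference shown in Step 4. Changing the protocol text also requires Ethics Committee approval before implementation under Protocol 14.3.

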### 17.1.3 Sensitivity Analysis Of Primary Efficacy Variables

In order to addressing robustness of the primary analysis results of primary efficacy endpoint, three sensitivity analysis approaches are proposed:

- **Sensitivity 1:** It will be conduct based on PPS. An ANOVA model on primary efficacy endpoints (reduction ratios of  $\lambda$  FLC and  $\beta 2$ -MG) with fixed effects for treatment group and study site to evaluate differences between the treatment groups

will be analyzed and corresponding two-sided 95% CIs derived. An interaction term between treatment group and study site will be tested. If the interaction between treatment group and study site is not significant ( $P>0.05$ ), then the interaction term will be removed from the model. Data will also be tested for normality using a Quantile-Quantile (Q-Q) plot. If data are not normally distributed, a log transformation will be used and if normality holds, the Cox method will be used to estimate two-sided 95% CIs. If after log transformation, measurements do still not follow a normal distribution, then the Kruskal Wallis test will be used in place of the ANOVA.

- **Sensitivity 2:** It will be conduct based on PPS. A non-parametric method: Wilcoxon Rank-Sum Test will be used to analyze the primary endpoints. Hodges-Lehmann estimate will be used to calculate the 95%CI.
- **Sensitivity 3:** Above statistical analysis method will be conducted using the FAS population with multiple imputation method based on missing at random (MAR) to impute the missing values of the  $\lambda$  FLC and  $\beta$ 2-MG RRs. A two-sample t-test will be utilized to generate a two-sided 95% confidence interval (CI) for the difference in means ( $\mu_T - \mu_R$ ). the imputing step is as follow:
  1. Handling baseline missing data. Baseline missing data will be imputed using regression imputation. Baseline value of age, gender, serum creatinine and bun will be incorporated into the model as covariates to predict and impute missing baseline values.
  2. The missing data are imputed by group in 20 times to generate 20 complete datasets using PROC MI procedure(seed=6162022) by monotone imputation.
  3. The primary endpoint will be calculated according to each imputed complete datasets.
  4. Two sample t-test as specified for primary analysis will be applied to each complete datasets and the inference drawn using Rubin's combination rules using PROC MIANALYZE.

- **Sensitivity 4:** tipping point approach will be used to assess the robustness of analysis result under missing not at random (MNAR) assumption. It will perform a series of

analyses with a range of different values of the shift parameter  $\delta$  only applied to the imputed datasets of Theranova 400 group at which the conclusion about the statistical significance of the estimated treatment effect will be altered. All step is same to Sensitivity 3 except that the shift parameter  $\delta$  will be added to the imputed datasets at the Theranova 400 group.

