#### **5.5 Scope of Study**

It is proposed to conduct this study in 11 medical institutions with qualifications for clinical studies.

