### 7.1.2 Rationale of Study Design

- (1) Selection of clinical study methods: randomized, parallel-controlled, open-label, multicenter study.
- (2) Randomization: In this trial, central randomization system is used for randomization, and stratified block randomization method is selected. Using the center as a stratification factor, all screened patients are randomly assigned to the test group or the control group at a ratio of 1:1.
- (3) Open-label: Investigators and patients are not blinded due to differences in the appearance and operation between investigational products and control products. In

addition, the RRs of  $\beta2$ -MG and  $\lambda$  FLC in this trial are not affected by subjectivity of investigators or patients, so an open-label design is utilized in this trial.

(4) Parallel control: There is no similar product available yet. The hollow fiber HD/filter (model: FX 800 HDF) is similar to the investigational product in intended uses, structures and performances as the control product in this trial.

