## 3.2 Sample Size Calculation

### 3.2.1 Total Sample Size

The goal of this study is to demonstrate non-inferiority of Theranova 400 compared to FX 800 in the 2 primary endpoints and the non-inferiority margins selected are considered clinically acceptable. The sample size calculation is performed using PASS procedure Mann-Whitney U or Wilcoxon Rank-Sum Tests for Non-Inferiority. A separate sample size calculation is performed for both primary endpoints using a specified non-inferiority margin of 10% and a one-sided alpha level of 0.025, where the true difference in means is assumed to be zero (0).

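### Sensitivity 1 lets a 5% interaction pre-test decide which treatment difference and CI it reports, and the SAP does not say how that difference is formed when the interaction stays

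*SAP*

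**What the plan says.** Protocol 8.7.1.1 lists, as a sensitivity analysis for both primary endpoints: "An ANOVA model with fixed effects for treatment group and study site to evaluate differences between the treatment groups will be analyzed". It has no interaction term.

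SAP 17.1.3, Sensitivity 1, fits the same ANOVA on the per-protocol set (PPS) and adds a step: "An interaction term between treatment group and study site will be tested". If that test gives P>0.05, "then the interaction term will be removed from the model". By implication the term stays at P≤0.05. For that case the SAP gives no site weights, no pooling of small sites and no rule for a site that has patients in only one arm.

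The primary analysis in SAP 17.1.2 is a two-sample t-test on the PPS without site. Study success (protocol 8.5, SAP 8.2) requires non-inferiority on both endpoints.

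**The concern.** In a treatment + site model, the treatment difference weights each site by its information. Once a treatment-by-site term is in the model, there is no single difference until site weights are chosen. If none are named, the usual output is the unweighted least-squares mean difference, in which a site with 4 patients counts as much as one with 60. The pre-test would then choose both the quantity estimated and the width of its CI.

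This matters because randomisation is stratified by center (protocol 7.1.2), and Sensitivity 1 is the only planned analysis of the primary endpoints that names site in its model. Its purpose is to test the robustness of the primary result, so readers will hold its CI against the same margins. It could disagree with the t-test merely because the weights changed.

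**Working it through.** **Inputs from the documents.** SD 9.09 (λ FLC) and 14.28 (β2-MG), SAP 3.2.2 and 3.2.3. Margins 3.783 and 7.848, protocol 8.5. True difference 0, SAP 3.2.1. 129 evaluable patients per arm and 5% loss, SAP 3.2.4. Sites, protocol 5.5: "It is proposed to conduct this study in 11 medical institutions with qualifications for clinical studies". Allocation, protocol 7.1.2: "all screened patients are randomly assigned to the test group or the control group at a ratio of 1:1", stratified by center. Error rates, protocol 8.3: "A 0.025 one-sided significance level and a power of 90% were used in planning this study".

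**Assumed, because the documents give no figure.** Site sizes; the between-site SD of the treatment effect (0, 2 or 4 points); equal site weights when the interaction stays.

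**The plan's own figures.** The t-test needs 123 per arm for λ FLC; dividing by the Wilcoxon efficiency 3/π gives 128.8, so 129. For β2-MG, 71 becomes 74.4, so 75. Then 129/0.95 = 135.8, so 136. All three agree with the plan.

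**Step 1: standard errors.** With nT and nR the patients per arm in a site:
- main effects: SE = SD / √Σ[nT·nR/(nT+nR)]
- interaction kept, equal weights: SE = (SD/11) × √Σ(1/nT + 1/nR)

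With equal arms within sites, the first sum is 129/2 = 64.5 whatever the site sizes, so the λ FLC main-effects SE is 9.09/√64.5 = 1.13. The 95% half-width is 1.97 × 1.13 = 2.23.

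For the second formula, three assumed patterns (patients per arm, each totalling 129):
- near-equal: eight sites of 12 and three of 11; Σ(1/nT+1/nR) = 1.879
- moderate: 24, 20, 17, 15, 13, 11, 9, 7, 6, 4, 3; sum 2.778
- skewed: 40, 28, 19, 13, 9, 7, 5, 3, 2, 2, 1; sum 5.955

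| Pattern | λ FLC SE, equal weights | Ratio to main effects | Half-width | Power (main effects 91.5%) |
|---|---|---|---|---|
| Near-equal | 9.09/11 × √1.879 = 1.13 | 1.00 | 2.23 | 91% |
| Moderate | 9.09/11 × √2.778 = 1.38 | 1.22 | 2.71 | 78% |
| Skewed | 9.09/11 × √5.955 = 2.02 | 1.78 | 3.97 | 46% |

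In the skewed pattern the λ FLC half-width exceeds the 3.783 margin. The β2-MG half-widths are 3.51, 4.26 and 6.24, against 3.50 for main effects and a margin of 7.848.

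Simulations with 272 patients, 5% random loss and total site sizes from 60 down to 4 give ratios of about 1.4 to 1.5. Sizes from 80 down to 2 give about 1.75 to 1.9. Only the extremes are fixed; the ranges cover different sizes in between.

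**Step 2: how often it matters with no true heterogeneity.** The term is then kept in about 5% of trials per endpoint. The loss is the retention rate times the drop in non-inferiority rate among retained trials (λ FLC, 20,000 simulated trials per pattern):
- moderate: 0.051 × (0.896 − 0.748) = 0.8 points (91.4% to 90.6%)
- skewed: 0.049 × (0.902 − 0.481) = 2.1 points (91.7% to 89.6%)

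A simulation of 4,000 trials per setting gives 92% against 92% with equal sites, 91% against 89% for sizes 60–4, and 92% against 89% for sizes 80–2 (main effects against the SAP rule).

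**Step 3: if the effect truly varies between sites.** For λ FLC the term is kept in about 13–16% of trials at a between-site SD of 2 and about 46–56% at 4. With mean difference 0, non-inferiority under the SAP rule against main effects is:
- sizes 60–4, SD 2: 83–84% against 87%
- sizes 60–4, SD 4: 71% against 79%
- sizes 80–2, SD 4: 61–63% against 76–77%

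**Step 4: non-estimability.** A site with an empty arm leaves the equal-weight difference undefined; the main-effects SE stays at 1.13. For sizes 80–2 an empty cell arises in about 10–11% of trials. A two-patient site with 5% loss alone gives 1 − 0.95² = 9.75%. It affects the reported result only if the term is also kept: 0.10 × 0.05 = 0.5% of trials with no heterogeneity, if the two are roughly independent.

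**The case against.** Most of the opposing case limits the size of the point.

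- **No decision depends on it.** This stands. Success rests on the PPS t-test. SAP 17.1.3 says only that CIs are derived for Sensitivity 1, so a reader who infers a formal pass/fail test against the margin goes beyond the text.
- **Equal weighting is not written in the SAP.** This stands. Observed-margin weights would also fit the wording. What the documents show is that no weights are named; equal weighting is the usual default.
- **The large losses rest on assumptions.** This stands. Site sizes and between-site SDs are not in the documents. An SD of 4 points exceeds the whole 3.783 margin, and the middle molecules are assayed centrally, which removes one source of site differences.
- **Non-estimability.** One might infer that about one trial in ten would lose this analysis. That is the rate of empty cells in one skewed pattern, before requiring that the interaction be kept. Center-stratified 1:1 allocation makes empty cells unlikely outside very small sites. The control-only 16 L exclusion from the PPS (SAP 6.2) could raise the rate and is not modelled here.
- **Undeclared change from the protocol.** SAP section 4 does not list the interaction step, so a reader might infer an unreported departure. This cannot be verified: SAP section 1 cites protocol V1.0, Amendment 1, and the protocol at hand is V1.1, Amendment 1.1. Protocol 8.1 also leaves analysis details to the SAP.
- **Part of the lost power is protection.** This stands. With the average-site difference set at −3.783 and SD 4, the main-effects CI falsely showed non-inferiority in 10.8% of simulated trials against 8.6% under the SAP rule (sizes 60–4), and in 14% against 8% (sizes 80–2).

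What remains is that the two documents describe different models, and that a pre-test selects an estimate the SAP does not define.

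**Conclusion.** The point holds as a moderate one about a robustness check. Under the default weighting, the retention rule lets the data choose what Sensitivity 1 estimates. The harm is nil with near-equal sites. With no true heterogeneity and strongly unequal sites it is about 2 to 3 percentage points in showing λ FLC non-inferiority, and more only if effects truly differ between sites. Losing the estimate altogether needs an empty arm-by-site cell and a retained interaction together, about 1% of trials or fewer without heterogeneity.

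These sizes rest on equal site weights, assumed site sizes and random loss. The documents do not support reading this as a threat to the primary conclusion.

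**What to change.** In SAP 17.1.3, Sensitivity 1, state that the treatment difference and 95% CI always come from the treatment + site main-effects model of protocol 8.7.1.1. Report the interaction p-value and a table of site-specific differences as a description of heterogeneity, and delete the keep/remove rule.

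This costs about one sentence, needs no extra data and keeps the interaction visible. The downside should be named in the SAP: if effects truly differ between sites, the main-effects CI weights sites by their information and is less conservative for an average-site effect. The site-specific table must therefore be shown beside it.
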